7.1. Disposition of Subjects and Withdrawals

All subjects who provide informed consent will be accounted for in this study.

The total number of subjects for each of the following categories will be presented overall for the enrolled population:

- Screening Population [REDACTED]
- Safety population (SAFT)
- Intent-to-treat Population (ITT)
- Per Protocol Population (PP)
- Subjects enrolled by site

[REDACTED]

[REDACTED]

[REDACTED]

[REDACTED]

The total number of screening failures and the reasons for screen failure will be presented overall.

7.2. Protocol Deviations

Protocol deviations will be identified and classified at the data review meeting before defining the analysis populations for the interim and the final analyses.

Only subjects with potentially important deviations as defined in the PDGP, will be discussed.

Important protocol deviations leading to exclusion of the PP population, i.e., major deviations, will be summarized by type of deviations for the ITT and SAFT populations. Deviations directly linked to COVID-19 will be reported and summarized separately.

All protocol deviations will be listed.

7.3. Demographics and Other Baseline Characteristics

Descriptive summaries of the demographics (age, sex, height, body weight, childbearing potential, ethnicity, race, Fitzpatrick skin type) will be completed for each of the following populations: ITT, SAFT, and PP.

For the continuous variables, the number of non-missing values and the mean, SD, minimum, median, and maximum will be tabulated.

Descriptive summaries of the medical/surgical history and prior medications will be completed for the Safety population.

Medical/surgical history will be coded with MedDRA dictionary. Incidences of findings in medical history will be summarized by SOC and PT, unless otherwise specified.

The frequency and percentage of prior medications for subjects in RHA [REDACTED] and No-treatment control groups will be summarized using the latest version available at time of the database lock of the World Health Organization Drug Dictionary (WHO-DD) by Anatomical Therapeutic Chemical (ATC) level 2 within level 1. [REDACTED]

7.4. Exposure and Compliance

Data will be tabulated for Safety population.

Number of treatment sessions will be tabulated in a frequency table for RHA [REDACTED] and No-treatment control groups.

[REDACTED]

[REDACTED]

Number of device malfunction reported by visit will be tabulated in a frequency table by treatment group.

All exposure data will be listed.

8. Effectiveness Analysis

All effectiveness analysis will be based on the ITT population. Primary endpoint and TIOHS responder as assessed by BLE analyses will be repeated for the PP population.

8.1. Primary Effectiveness Analysis

Primary endpoint:

Primary endpoint is the responder rate after 12 weeks.

A responder is defined as a subject with an absolute ≥ 1 -grade improvement in both eyes on the TIOHS as assessed by the BLE from before initial treatment to 12 weeks after the initial treatment (Visit 5). A negative change from Baseline value is considered as an improvement. Subject with missing assessment for at least one eye at Visit 5 will be considered as a non-responder.

Responder rate at Visit 5 as assessed by the BLE will be tabulated by treatment group: frequency of responders, percentage of responders along with 95% CI will be tabulated. Fisher's exact test will be performed to compare responder rates between RHA [REDACTED] and the No-treatment control group. Test will be one-sided with a Type I error rate at 0.025. To achieve superiority, the observed P value must be ≤ 0.025 .

[REDACTED]

Missing data will be handled as described in section 6.1.3.1.

Additionally, the following 2 conditions must be met:

- At least 70% of the subjects treated with RHA [REDACTED] must be responders
- The difference between the responder rate for subjects treated with RHA [REDACTED] and the No-treatment control group must be $\geq 50\%$ points.

Co-primary endpoint:

The co-primary endpoint will be the change from Baseline in the modified FACE-Q "Appraisal of lower eyelids" domain score [REDACTED]

[REDACTED] and the average change from Baseline of the modified FACE-Q "Appraisal of lower eyelids" converted raw score at 12 weeks. Missing data will be handled as described in section 6.1.3.1.

[REDACTED]

Superiority will be declared if:

- the lower bound of 2-sided 95% confidence interval for the responder rate for RHA [REDACTED] is at least 70%, and
- the lower bound of 2-sided 95% confidence interval for the difference in the responder rate between subjects treated with RHA [REDACTED] and the No-treatment control group is at least 50%, and
- the lower bound of 2-sided 95% confidence interval for the modified FACE-Q “Appraisal of lower eyelids” raw score for RHA [REDACTED] is at least 3, and
- the lower bound of 2-sided 95% confidence interval for the difference in mean change from Baseline of the modified FACE-Q between RHA [REDACTED] treated group and the No-treatment control group is at least 12.

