2.2. Study Endpoints

2.2.1. Effectiveness Endpoints

2.2.1.1. Primary Effectiveness Endpoint

The primary effectiveness endpoint of this study is the responder rate after 12 weeks.

The effectiveness of RHA [REDACTED] will be demonstrated if the responder rate for subjects treated with RHA [REDACTED] is statistically superior to the responder rate for subjects of the No-treatment control group 12 weeks (Visit 5) after randomization as assessed by the Blinded Live Evaluator (BLE) using the live-validated TIOHS. [REDACTED]

Additionally, the following 2 conditions must be met:

- The responder rate for RHA [REDACTED] is $\geq 70\%$
- The difference between the responder rate for subjects treated with RHA [REDACTED] and the No-treatment control group is $\geq 50\%$.

A responder will be defined as a subject with a ≥ 1 -grade improvement in both eyes on the TIOHS as assessed by the BLE from before initial treatment and 12 weeks after the initial treatment (Visit 5).

The co-primary endpoint will be the change from Baseline in selected questions of the FACE-Q “Appraisal of lower eyelids” domain score at 12 weeks. The effectiveness of RHA [REDACTED] will be demonstrated if the modified FACE-Q “Appraisal of lower eyelids” change from Baseline score (converted to a 0-100 scale – Rasch conversion) for subjects treated with RHA [REDACTED] is statistically superior (by at least 12 points) to the subjects of the No-treatment control group 12 weeks (Visit 5) after randomization [REDACTED]

Additionally, the following 2 conditions must be met:

- The mean change from Baseline of the modified FACE-Q “Appraisal of lower eyelids” raw score for RHA [REDACTED] is ≥ 3
- The difference between the modified FACE-Q “Appraisal of lower eyelids” change from Baseline for subjects treated with RHA [REDACTED] and the No-treatment control group is ≥ 12 .

[REDACTED] Subjects randomly assigned to the No-treatment control group will receive treatment in Phase 1b, but these data will not be pooled for the primary endpoint analysis.

Superiority will be declared if:

- the lower bound of 2-sided 95% confidence interval for the responder rate for RHA [REDACTED] is at least 70%, and
- the lower bound of 2-sided 95% confidence interval for the difference in the responder rate between subjects treated with RHA [REDACTED] and the No-treatment control group is at least 50%, and

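### The responder success thresholds are stated both as observed values and as lower 95% confidence bounds, and no visible text says that the lower-bound list decides

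*SAP*

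**What the plan says.** **Observed-value set.** Section 2.2.1.1 treats the device's effectiveness as shown if the RHA responder rate is statistically superior to control. It then adds "Additionally, the following 2 conditions must be met": an RHA rate of at least 70% and a difference of at least 50%. Section 8.1 makes this operational with a one-sided Fisher's exact test (P at most 0.025, described there as what superiority needs), together with "At least 70% of the subjects treated with RHA [REDACTED] must be responders" and a difference between RHA "and the No-treatment control group must be $\geq 50\%$ points". For FACE-Q, section 2.2.1.1 asks for a mean raw-score change of at least 3 and a difference between RHA "and the No-treatment control group is ≥ 12".

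**Lower-bound set.** Both sections then list when superiority is declared. The list requires that "the lower bound of 2-sided 95% confidence interval for the responder rate for RHA [REDACTED] is at least 70" percent, and that "the lower bound of 2-sided 95% confidence interval for the difference in the responder rate between subjects treated with RHA" and control is at least 50%. The FACE-Q items use lower bounds of 3 (raw score) and 12 (difference). The Fisher P value is not in this list.

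**Overall sentence.** Near its end, section 8.1 allows overall superiority only if all superiority criteria are met on both endpoints. It does not enumerate those criteria.

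**The concern.** An observed rate of 70% and a lower 95% bound of 70% are different bars. The two sets use the same thresholds, are attached to different conclusions (effectiveness shown; superiority declared), and are not ranked in the visible text. Section 8.1 also uses the word superiority for both the Fisher result and the lower-bound list.

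This is the pass/fail rule of a trial meant to support a premarket application (section 1.1). If a result falls between the bars, section 2.2.1.1 can be cited for success and the lower-bound list for failure, after the data are known. The chance of success also depends on which bar applies.

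**Working it through.** **Inputs.** Total 258 (section 3.3) and allocation 3:1 (section 3.1) give 193.5 to 64.5, so the arms are 194/64 or 193/65. All subjects are assumed evaluable. No interval method, responder-rate assumption, SD or power statement is visible. Several interval methods are therefore used, and true rates and SDs are assumptions. For the same reason the figure of 258 cannot be reproduced, which is not held against the plan.

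**1. RHA rate.** Smallest number of responders that passes:

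| RHA n | Observed ≥ 70% | Lower bound ≥ 70%, Clopper-Pearson or Wilson | Lower bound ≥ 70%, Wald |
|---|---|---|---|
| 194 | 136 (70.1%) | 149 (76.8%) | 148 (76.3%) |
| 193 | 136 (70.5%) | 148 (76.7%) | 147 (76.2%) |

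**2. Difference.** With 10/64 control responders (15.6%), a lower bound of 50 points needs 149/194 by Wald (observed difference 61.2 points) or 152/194 by Newcombe (62.7 points), not 50.

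**3. One result under both sets: 145/194 against 10/64.**
- Rates are 145/194 = 74.7% and 10/64 = 15.6%. The difference is 59.1 points and the one-sided Fisher P is about 4 × 10⁻¹⁷. All observed-value responder conditions are met.
- Lower bound of the rate: 68.0% (Clopper-Pearson), 68.2% (Wilson), or 0.7474 − 1.96 × 0.0312 = 68.6% (Wald). All are below 70%.
- Lower bound of the difference, Wald: 0.5912 − 1.96 × √(0.7474 × 0.2526/194 + 0.1563 × 0.8438/64) = 0.5912 − 1.96 × 0.0551 = 48.3 points.
- Lower bound of the difference, Newcombe: 0.5912 − √[(0.7474 − 0.6819)² + (0.2643 − 0.1563)²] = 46.5 points. Both are below 50.

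**4. Chance of meeting both responder conditions.** Exact joint binomial enumeration, Clopper-Pearson for the rate and Newcombe for the difference:

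| Assumed true rates | 193/65: observed | 193/65: lower bounds | 194/64: observed | 194/64: lower bounds |
|---|---|---|---|---|
| 75% v 15% | 91.1% | 19.2% | 92.3% | 18.8% |
| 80% v 15% | 99.6% | 65.1% | 99.6% | 64.6% |
| 85% v 15% | 100.0% | 92.0% | 100.0% | 91.3% |
| 85% v 10% | 100.0% | 99.4% | 100.0% | 99.3% |

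No outcome passes the lower bounds and fails the observed values. The sets are nested.

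**5. FACE-Q, over assumed SDs.**
- Difference: 12 + 1.97 × SD × √(1/194 + 1/64) = 12 + 0.284 × SD. This gives 16.3, 17.7, 19.1 and 20.5 points for SDs of 15, 20, 25 and 30.
- Raw score: 3 + 1.972 × SD/√194. This gives 3.42 to 3.85 for SDs of 3 to 6. The lower-bound item omits the word change; it is read here as the same mean change that the observed-value item names.

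**The case against.** The best defence is that the text can be read cumulatively. In section 8.1 the P value and the observed values are worded as necessary conditions, the lower-bound list is what triggers the declaration, and the overall sentence requires all superiority criteria. Because the sets are nested, that reading gives one answer: the lower bounds decide. Section 2.2.1.1 can be read the same way if its own superiority list defines what statistically superior means. This largely stands. A reader might infer two rival rules of equal standing, and the documents do not support that.

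Three further limits stand.
- The 12-point part is weaker. Sections 1.2 and 2.2.1.1 describe FACE-Q superiority by a 12-point amount, which may already be a margin test, and visible section 8.1 has no observed-value FACE-Q condition.
- The gap is large only when the true rates lie near the thresholds.
- Text is blacked out around these criteria, so the missing ranking can be asserted only of what is visible. A reader might also infer that the trial is underpowered or was sized for the looser bar. No visible power text supports that, and 258 may already rest on the lower bounds.

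The defence does not remove the defect. The overall sentence does not say which criteria it counts, section 8.1 attaches superiority to the Fisher P value as well, and section 2.2.1.1 gives the first set its own conclusion. On the cumulative reading, the observed-value conditions can never change the outcome, yet they are written as requirements.

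**Conclusion.** The point holds as a defect in the stated decision rule. The 70% and 50-point thresholds appear at two bars in sections 2.2.1.1 and 8.1. The raw-score threshold of 3 is double-stated in 2.2.1.1, and the 12-point threshold arguably so. The lower-bound reading is the better supported one, but it has to be inferred.

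For about 194 RHA subjects the bars are roughly 70% and 77% observed. For the difference, with controls near 15%, they are 50 and about 61 to 63 points. At assumed true rates of 75% v 15% the two sets disagree in about 72% of trials (91.1% − 19.2%); at 85% v 10%, in under 1%. These figures rest on the 3:1 split of 258, complete data and the interval methods named. Every method tried shows the gap in the bars.

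**What to change.** In sections 2.2.1.1 and 8.1, state one rule: success requires all four lower-95%-bound criteria. Mark the observed-value conditions as supportive, since the lower bounds imply them, and do the same for the Fisher test against a zero difference, which a lower bound of 50 points already settles. Tie the conclusion about effectiveness in 2.2.1.1 to the same rule, and say that the raw-score criterion refers to the mean change. Align section 1.2, and confirm that 258 was derived under the lower-bound rule.

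The cost is SAP wording, to be settled before unblinding. The downside is that the stated bar is then visibly the stricter one. If the size turns out to have been planned on observed values, its power would need restating.

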8.3. Secondary Effectiveness Analysis

Secondary endpoints will be analyzed [REDACTED]

- Analysis of data from Visit 1/Visit 1b to Visit 11 with all subjects pooled together.

8.3.1. TIOHS Assessed by BLE, [REDACTED]

Summary statistics (mean, minimum, maximum, SD, and 95% CI of the mean, change from Baseline) will be calculated and presented per eye for each study visit. [REDACTED]

The TIOHS is a subjective 5-grade static scale as detailed below, will be assessed by TI and BLE.

Grade description:

Grade 0 - None

Grade 1 - Minimal

Grade 2 - Moderate

Grade 3 – Severe

Grade 4 - Very severe.

Relative frequency will be based upon the total number of subjects with non-missing data for the observation at the specific visit.

[REDACTED]

8.3.2. Responder Rate Based on TIOHS by BLE

Responder rate defined as both eyes with an absolute ≥ 1 -grade improvement from Baseline on the TIOHS will be tabulated by treatment group: frequency of responders, percentage of responders along with 95% CI will be tabulated. Fisher's exact test will be performed to compare responder rates at each applicable visit.

The following categories are used:

- Responder
- Non-responder

Responder rate calculation will be based upon the total number of subjects with non-missing data for the observation at the specific visit.

A figure will be created by treatment arm for TIOHS grade responder rate assessed by BLE and TI as well. The figure will represent responder rate at each time point along with 95% confidence intervals for each treatment arm.

8.3.3. FACE-Q

For FACE-Q "Appraisal of lower eyelids", the outcome of all the question will be pooled and data will be transformed so that higher scores reflected superior (positive) outcome and adapted to a scale of 100 units (i.e., worst/lowest score = 0, best/highest score = 100) as per section 6.1.6.2. Total raw score, total converted raw score and Rasch converted score will be presented.

Only 7-item FACE-Q "Appraisal of lower eyelids" will be presented.

Mean, SD, 95% CI of the mean, median, min-max, change from Baseline, 95% CI for change from Baseline will be summarized by treatment arm. FACE-Q scale score change from Baseline values at each visit will be compared between treatment arms by t test or, in case normality assumption is not met, Wilcoxon-Mann-Whitney test. *P* values will be presented in the summary table.

A summary table with number of subjects answering each possibility by question will also be provided by visit.

[REDACTED]

8.3.4. GAIS Assessed by [REDACTED] BLE and Subject

The GAIS is a subjective 5-grade dynamic scale as detailed below and will be assessed by

Investigators and subjects.

Grade description:

1. Much improved
2. Improved
3. No change
4. Worse
5. Much worse.

GAIS grade frequencies and percentages will be calculated and presented for each scheduled study visit.

Additionally, proportions of “improved” and “much improved” (GAIS responder rate) will be presented, along with the 95% CI of the proportion at each applicable study visit and for each evaluators.

For GAIS assessed by BLE, [REDACTED] and subject, Fisher’s exact test will be performed to compare responder rates at each applicable visit .

Relative frequency and responder rate calculation will be based upon the total number of subjects with non-missing data for the observation at the specific visit.

A figure will be created by treatment arm for GAIS responder rate assessed by BLE, [REDACTED] and subject as well. The figure will represent responder rate at each time point along with 95% confidence intervals, for each treatment arm.

8.3.5. Subject Satisfaction Score

Subject Satisfaction will be assessed by subjects using the following static 5-grade scale.

Grade description:

1. Very satisfied
2. Satisfied
3. Neither satisfied nor dissatisfied
4. Dissatisfied
5. Very dissatisfied.

Satisfaction grade frequencies and percentages will be calculated and presented for each scheduled study visit.

For subject satisfaction, proportions of “satisfied” and “very satisfied” (subject satisfaction responder rate) will be presented, along with the 95% CI of the proportion at each applicable study visit. Fisher’s exact test will be performed to compare responder rates at each applicable visit.

A series of 15 horizontal black bars of varying lengths, arranged vertically. The lengths of the bars decrease from top to bottom, creating a descending staircase effect. The bars are set against a white background.

9. Safety and Tolerability Analysis

All safety analyses will be performed on the Safety population.

9.1. Adverse Events

All AEs will be coded using the MedDRA dictionary.

Number of all AEs, ADEs, [REDACTED] and number and percentage of subjects having the specific AEs will be presented. 2-sided exact 95% CIs will be calculated for the proportion of subjects having the specific AEs.

All AEs reported during the study will be described by SOC and PT.

Incidence rates defined as number of subjects presenting the AE divided by the number of subjects in the treatment group with 2-sided exact 95% CIs will be calculated for the overall incidence of AEs, ADEs, [REDACTED]

The causal relationship of the AE to the study treatment is determined by the investigator by relationship to the study procedure and relationship to the study device [REDACTED]

[REDACTED]

[REDACTED]

[REDACTED]

[REDACTED]

[REDACTED]

[REDACTED]

[REDACTED]

[REDACTED]

A document page with several large black rectangular redactions covering the majority of the text area. The redactions are irregular in shape, suggesting redacted content.

Individual listings of all AE data will also be given.

9.1.1. Deaths

All deaths occurring during the study will be listed.

9.2. CTRs

Number of all CTRs and number and percentage of subjects having the specific CTR will be presented for each injection. [REDACTED]

CTRs to be reported are the following;

- Redness
- Pain
- Tenderness
- Firmness
- Swelling
- Lumps/Bumps
- Bruising
- Itching
- Discoloration

[REDACTED]

[REDACTED]

[REDACTED]

[REDACTED]

[REDACTED]

[REDACTED]

9.3. Clinical Laboratory Evaluations

Urine Pregnancy Test (UPT) for women of childbearing potential will be listed.

[REDACTED]

A horizontal bar chart consisting of 15 black bars of varying lengths, arranged in two groups. The top group contains 8 bars, and the bottom group contains 7 bars. The bars are positioned on a white background.

10. COVID-19 Impact

Visits and assessments impacted by the COVID-19 pandemic will be listed.

AD-ST-33.06 Effective date: 12-Nov-2020

[REDACTED]

11. Changes from Protocol

Not applicable.

12. Changes from Planned Analysis

Not applicable.

[REDACTED]

14. Tables, Listings, and Figures

All listings, tables, and graphs will have a header showing the sponsor company name and protocol and a footer showing the version of SAS, the file name and path, and the source of the data (eCRF page or listing number).

[REDACTED]

[REDACTED]

[figure not shown]
[REDACTED]

[REDACTED]

AD-ST-33.06 Effective date: 12-Nov-2020

Statistical Analysis Plan

Protocol Number

[figure not shown]
Statistical Analysis Plan

Protocol Number

[figure not shown]
Statistical Analysis Plan

Protocol Number

Statistical Analysis Plan

Protocol Number

Statistical Analysis Plan

Protocol Number

Statistical Analysis Plan

Protocol Number

Statistical Analysis Plan

Protocol Number

Statistical Analysis Plan

Protocol Number

Statistical Analysis Plan

Protocol Number

Statistical Analysis Plan

Protocol Number

[figure not shown]

Figure 1: Standardized Layout

<Sponsor Name>	Page xx of xx
Protocol: <protocol id>	Version

 xx.x.x
 
<Title of Table Listing or Figure>
 
<Study Population and if applicable subgroup Description>
 <hr/>	
Body of Table, Listing or Figure	
<hr/> 
<Note: If directly Applicable>
 
Footnote 1 <if applicable> Recommendation is to keep footnotes to a minimum
 
Footnote 2 <if applicable>
 
Footnote n <if applicable>
 
Footnote n+1 <pgm path and name>, <date>
	

Statistical Analysis Plan
Protocol Number

15.2. Planned Table Shells

Will be provided in separate document.

Statistical Analysis Plan
Protocol Number

15.3. Planned Listing Shells

Will be provided in separate document.

Statistical Analysis Plan
Protocol Number

[figure not shown]
15.4. Planned Figure Shells

Will be provided in separate document.

Statistical Analysis Plan

[figure not shown]
Protocol Number

Statistical Analysis Plan

Protocol Number

Statistical Analysis Plan

Protocol Number

Statistical Analysis Plan

Protocol Number

AD-ST-33.06 Effective date: 12-Nov-2020

Version 6.0 | Date 24-Apr-2024| AD-PR-109.02 Effective date: 17-Aug-2020

Page 66 of 72

Statistical Analysis Plan

Protocol Number

[REDACTED]

[REDACTED]

[REDACTED]

[figure not shown]
[REDACTED]

[REDACTED]

Statistical Analysis Plan

Protocol Number

AD-ST-33.06 Effective date: 12-Nov-2020

[figure not shown]
Version 6.0 | Date 24-Apr-2024| AD-PR-109.02 Effective date: 17-Aug-2020

Page 68 of 72

Statistical Analysis Plan

Protocol Number

AD-ST-33.06 Effective date: 12-Nov-2020

[figure not shown]
Version 6.0 | Date 24-Apr-2024| AD-PR-109.02 Effective date: 17-Aug-2020

Page 69 of 72

Statistical Analysis Plan

Protocol Number

[figure not shown]
AD-ST-33.06 Effective date: 12-Nov-2020

Version 6.0 | Date 24-Apr-2024| AD-PR-109.02 Effective date: 17-Aug-2020

Page 70 of 72

Statistical Analysis Plan

Protocol Number

Statistical Analysis Plan

Protocol Number
